2.8.3 Biomarker analyses

[figure not shown]
This section outlines the planned analyses for biomarkers related to Hidradenitis Suppurativa (HS). The analyses aim to characterize the effect of SAR442970 on pre-defined biomarkers in participants with HS and to evaluate the pharmacodynamic effect of SAR442970.

Unless otherwise specified, all data will be summarized in the safety populations of Period A and Period B. The continuous data will be summarized using the number of non-missing values (including the ones <LLOQ and >ULOQ), number of values under the limit of quantitation (LLOQ) if applicable, arithmetic mean, geometric mean, standard deviation, median, Q1, Q3, minimum and maximum. Categorical and ordinal data will be summarized using the count and percentage of non-missing, as appropriate.

The analysis will focus on markers associated with HS and SAR442970 activity, to be included in the Clinical Study Report (CSR). This analysis will include:

- Serum PD: sTNF and s OX40L measured at baseline, at week 4, at week 10, at Week 16, at Week 28 (EOT) and at week 36 (EOS).
- Serum: Lipocalin-2, CRP, hsCRP, SAA, ASCA, ACPA and YKL40 measured at baseline, at week 4, at week 12, at Week 16 and at Week 28 (EOT).
- Blood: Absolute neutrophil count, ESR measured at baseline, at week 4, at week 12, at Week 16 and at Week 28 (EOT).
- Plasma: IL-6 (Olink48) and CXCL13 measured at baseline, at week 4, at week 12, at Week 16 and at Week 28 (EOT).

Exploratory analyses, which will be detailed separately from the CSR, including but not limited to

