| Serum Anti-Drug Antibodies ee, ff       |   | X   | X            | X            |              |              |              |              |              | X             |                  |  |  |               |                  | X                | X                |  |   |
| Serum PD Biomarkers ee, ff, gg          |   | X   |              | X            |              |              | X            |              |              | X             |                  |  |  |               |                  | X                | X                |  |   |
|  |   |   |              |              |              |              |              |              |              |               |                  |  |  |               |                  |                  |                  |  |   |

| Procedure a                       | Screening Period (Maximum 4 weeks) b | Treatment Period A: Double-blind Placebo Controlled Study – Primary Efficacy Assessment Window (16 weeks) |              |              |              |              |              |              |              |               |                  | End of Double-blind/ Start of Open Label | Treatment Period B: Open Label Period (12 weeks) |               |                  |                  |                  | End of Open Label/ Start of Safety Follow-Up | Follow-Up Period C: Safety Follow-Up Period (8 weeks after EOT) |
|--|---|---|--------------|--------------|--------------|--------------|--------------|--------------|--------------|---------------|------------------|--|--|---------------|------------------|------------------|------------------|--|---|
| Visit Number (V) c                | V1  | V2  | V3           | V4           | V5           | V6           | V7           | V8           | V9           | V10           | V11              | V12                                      | V13  | V14           | V15              |                  |                  |  |   |
| Visit Label                                  | Screening                                       | Baseline  |              |              |              |              |              |              |              |               |                  |  |  |               |                  | EOT d | EOS d |  |   |

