*bb* Hidradenitis Suppurativa Clinical Parameters will be performed at each designated study visit and must address all relevant anatomical regions in each participant; the number, location, longest distance between relevant lesions, and whether the lesions are separated by normal-appearing skin will be measured in each anatomical area ; Hurley Stage is included as an assessment performed during the HS clinical parameters; Hidradenitis Suppurativa Physician's Global Assessment is included as an assessment performed during the HS clinical parameters. The site is responsible for counting lesions that received intervention as permanently present in the lesion counts from the date of the intervention. The data collected from the HS clinical parameters will be used for the derivation of the HiSCR50, HiSCR75, HiSCR90, IHS4, AN count, Hidradenitis Suppurative Physician's Global Assessment, raw counts, and disease flares. For each participant it is recommended that the HS Clinical Parameters is assessed by the same Investigator during the entire study if possible.

*cc* Investigator review of participant daily analgesic use diary.

*dd* The participant should complete the questionnaire before site personnel perform any clinic assessments and before any interaction with the site personnel has occurred to avoid biasing the participant's response.

*ee* Number of samples (tubes) and quantity of biological samples needed for each assessment can be found in the laboratory manual.

*ff* Up to 4 hours prior to IMP administration.

*gg* PD biomarkers will include serum TNF and serum OX40L.

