| Visit Days                                   | D-28 to D-1                                     | D1  | D15 (±3d) | D29 (±3d) | D43 (±3d) | D57 (±3d) | D71 (±3d) | D85 (±3d) | D99 (±3d) | D113 (±3d) | D127 (±3d)       |   | D141 (±3d)                                       | D155 (±3d)  | D169 (±3d) | D183 (±3d)       | (±3d)  | (±5d)   |
| Serum PD Biomarkers ff, gg, hh    |   | X   |           | X         |           |           | X         |           |           | X          |                  |   |  |   |            |                  | X  | X   |
| Plasma Biomarker Panel ff, gg, jj |   | X   |           | X         |           |           |           | X         |           | X          |                  |   |  |   |            |                  | X  |   |
| Serum Biomarker Panel ff, gg, jj  |   | X   |           | X         |           |           |           | X         |           | X          |                  |   |  |   |            |                  | X  |   |
|  |   |   |           |           |           |           |           |           |           |            |                  |   |  |   |            |                  |  |   |
|  |   |   |           |           |           |           |           |           |           |            |                  |   |  |   |            |                  |  |   |
|  |   |   |           |           |           |           |           |           |           |            |                  |   |  |   |            |                  |  |   |

| Procedure b        | Screening Period (Maximum 4 weeks) c | Treatment Period A: Double-blind Placebo Controlled Study – Primary Efficacy Assessment Window (16 weeks) |           |   |           |           |           |           |           |            |                  | End of Double-blind/ Start of Open Label  | Treatment Period B: Open Label Period (12 weeks) |                  |   |                  | End of Open Label/ Start of Safety Follow-up | Follow-Up Period C: Safety Follow-Up Period (8 weeks after EOT) |
|-------------------------------|---|---|-----------|---|-----------|-----------|-----------|-----------|-----------|------------|------------------|---|--|------------------|---|------------------|--|---|

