2.8.3.1 Biomarkers-specific analyses

2.8.3.1.1 Blood biomarkers

Analysis of blood biomarkers will be performed for markers associated with HS and/or SAR442970 activity, including:

- sTNF (soluble Tumor Necrosis Factor)
- sOX40L (soluble OX40 Ligand)
- Lipocalin-2
- CRP (C-Reactive Protein)
- hsCRP (High-Sensitivity C-Reactive Protein)
- SAA (Serum Amyloid A)
- ASCA (Anti-Saccharomyces cerevisiae antibodies)
- ACPA (Anti-Citrullinated Protein Antibodies)
- Absolute neutrophil count
- ESR (Erythrocyte Sedimentation Rate)
- IL-6 (Interleukin-6)
- CXCL13 (C-X-C Motif Chemokine Ligand 13)
- YKL40

For all the blood biomarkers,

- descriptive statistics at baseline and under treatment (table),
- boxplots and/or time profile plots (means \pm SEM)

will be reported by the study intervention group at each visit in both Periods A and B. Both the raw analysis values, change and percent change from baseline will be reported. Data will be log-transformed as appropriate.

Additionally, for period B, fold change, percent change, and absolute change from Week 16 to Week 28 will be calculated for all biomarkers mentioned above. These analyses will compare participants from period A and B. Also, for sTNF and sOX40L, fold change, percent change, and absolute change from Week 16 to Week 36 will also be presented for both groups of participants.

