A measurement (scheduled or unscheduled) will be used if it is available and measurement date is within the analysis window.

After applying these time windows, if multiple assessments are associated to the same time point, the closest from the targeted study day will be used. If the difference is a tie, the value after the targeted study day will be used. If multiple valid values exist within a same day, then the first value of the day will be selected. For procedures planned on Visit 2, if it is done on the same date as the first IMP injection but the performance time is missing, it will belong to the Visit 2 window.

If there is no measurement for a given parameter in an analysis window, data will be considered missing for the corresponding visit.

Table 12 - Analysis window definition for safety analysis

Analysis visits	Targeted study day ^a	Time window				
		Vital signs	Fasting lipid panel	Non-fasting laboratory tests	Urinalysis	12-lead ECG
Period A						
Screening	-28 to -14	<-14	<-14	<-14	<-14	<-14
Baseline	1	-14 - 1	-14 - 1	-14 - 1	-14 - 1	-14 - 1
Week 2	15	2 - 21	2 - 21	2 - 21	2 - 21	2 - 21
Week 4	29	22 - 35	22 - 35	22 - 35	22 - 35	22 - 35
Week 6	43	36 - 49	36 - 49	36 - 49	36 - 49	36 - 49
Week 8	57	50 - 63	50 - 63	50 - 63	50 - 63	50 - 63
Week 10	71	64 - 77	64 - 77	64 - 77	64 - 77	64 - 77
Week 12	85	78 - 91	78 - 91	78 - 91	78 - 91	78 - 91
Week 14	99	92 - 105	92 - 105	92 - 105	92 - 105	92 - 105
Week 16	113	106 - D ^b	106 - D ^b	106 - D ^b	106 - D ^b	106 - D ^b
Period B						
Week 18	15	2 - 21	2 - 21	2 - 21	2 - 21	2 - 21
Week 20	29	22 - 35	22 - 35	22 - 35	22 - 35	22 - 35
Week 22	43	36 - 49	36 - 49	36 - 49	36 - 49	36 - 49
Week 24	57	50 - 63	50 - 63	50 - 63	50 - 63	50 - 63
Week 26	71	64 - 77	64 - 77	64 - 77	64 - 77	64 - 77
Week 28	85	78 - 112	78 - 112	78 - 112	78 - 112	78 - 112
Week 36	141	>112	>112	>112	>112	>112

a Day 1 in Period A is the day of the first blinded IMP administration (or the day of randomization for participant not exposed).

Day 1 in Period B is the day of the first open-label IMP administration.

b Last window in Period A is the 1st dose of open-label IMP administration.

Table 13 - Analysis window definition for efficacy endpoints

Analysis visit	Targeted study day ^a	Time windows			
		HS clinical parameters	Dermatology Life Quality Index	Hidradenitis Suppurativa Quality of Life	
Period A					
Screening	-28 to -14	<-14	<-14		<-14
Baseline	1	-14 - 1	-14 - 1		-14 - 1
Week 2	15	2 - 21	2 - 21		2 - 21

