Week 4	29	22 - 42	22 - 42		22 - 42
Week 6	43				
Week 8	57	43 - 70	43 - 70		43 - 70
Week 10	71				
Week 12	85	71 - 98	71 - 98		71 - 98
Week 14	99				
Week 16	113	99 - D ^b	99 - D ^b		99 - D ^b
Period B					
Week 18	15				
Week 20	29	2 - 42	2 - 42		2 - 42
Week 22	43				
Week 24	57	43 - 70	43 - 70		43 - 70
Week 26	71				
Week 28	85	>70	>70		>70

^a Day 1 in Period A is the day of the first blinded IMP administration (or the day of randomization for participant not exposed). Day 1 in Period B is the day of the first open-label IMP administration.

^b Last window in Period A is the 1st dose of open-label IMP administration.

Table 14 - Analysis window definition for daily questionnaires

Analysis visit	Targeted study day ^a	Time windows		
		Daily Diary HS-Skin Pain NRS	Daily Diary PP-NRS	Daily diary analgesic use
Period A				
Screening	-28 to -7	<-7	<-7	<-7
Baseline	1	-7 - <1	-7 - <1	-7 - <1
Week 2	15	8 - 14	8 - 14	8 - 14
Week 4	29	22 - 28	22 - 28	22 - 28
Week 6	43	36 - 42	36 - 42	36 - 42
Week 8	57	50 - 56	50 - 56	50 - 56
Week 10	71	64 - 70	64 - 70	64 - 70
Week 12	85	78 - 84	78 - 84	78 - 84
Week 14	99	92 - 98	92 - 98	92 - 98
Week 16	113	106 - D ^b	106 - D ^b	106 - D ^b
Period B				
Week 18	15	8 - 14	8 - 14	8 - 14
Week 20	29	22 - 28	22 - 28	22 - 28
Week 22	43	36 - 42	36 - 42	36 - 42
Week 24	57	50 - 56	50 - 56	50 - 56
Week 26	71	64 - 70	64 - 70	64 - 70
Week 28	85	78 - 84	78 - 84	78 - 84

a Day 1 in Period A is the day of the first blinded IMP administration (or the day of randomization for participant not exposed). Day 1 in Period B is the day of the first open-label IMP administration.

b D = minimum (Day 112, the day prior to the first open-label IMP)

Table 15 - Analysis windows for pharmacokinetics/pharmacodynamics variables

Analysis visit	Targeted study day ^a	Time windows				
		ADA	Blood biomarkers	PK	PD Biomarker	Skin Biopsy
Period A						
Screening	-28 to -14	<-14	<-14		<-14	
Baseline	1	-14 - 1	-14 - 1	≤1	-14 - 1	≤1
Week 2	15	2 - 21	2 - 21		2 - 21	
Week 4	29	22 - 42	22 - 42	2 - 49	22 - 42	
Week 6	43					
Week 8	57	43 - 70	43 - 70	50 - 63	43 - 70	
Week 10	71			64 - 77		
Week 12	85	71 - 98	71 - 98	78 - 98	71 - 98	
Week 14	99					
Week 16	113	99 - D ^b	> 1			
Period B						
Week 18	15			2 - 21		
Week 20	29	2 - 42	2 - 42	22 - 70	2 - 42	
Week 22	43					
Week 24	57	43 - 70	43 - 70		43 - 70	
Week 26	71					
Week 28	85	71 - 112	> 70	71 - 112	71 - 112	
Week 36	141	> 112		> 112	> 112	

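### Serum TNF and OX40L are drawn at Week 10, but the SAP's PD windows have no Week 10, so those samples are labelled Week 8 or Week 12

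*SAP*

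**What the plan says.** **Sampling.** SAP 2.8.3 states that soluble TNF and OX40L are "measured at baseline, at week 4, at week 10, at Week 16", followed by Week 28 (EOT) and Week 36 (EOS). The protocol agrees. In the rows "Serum PD Biomarkers ee, ff, gg" (Section 1.3.1, non-US) and "Serum PD Biomarkers ff, gg, hh" (Section 1.3.2, US) there is a mark at Weeks 0, 4, 10 and 16, EOT and EOS, and none at Weeks 8 or 12. The footnote to the first row confirms which markers are meant: "PD biomarkers will include serum TNF and serum OX40L". Both schedules put Week 10 at Day 71 ± 3 days.

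**Windows.** In SAP 4.4, "Table 15 - Analysis windows for pharmacokinetics/pharmacodynamics variables" has its own PD Biomarker column. For Period A it gives Week 2 as Days 2–21, Week 4 as Days 22–42, Week 8 as Days 43–70, Week 12 as Days 71–98, and Week 16 from Day 99. The Week 10 row (target Day 71) has one entry, 64–77, in the PK column.

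**Allocation rule.** SAP 4.4 assigns samples by date: "A measurement (scheduled or unscheduled) will be used if it is available and measurement date is within the analysis window". A visit with no value in its window is treated as missing.

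**Use.** SAP 2.8.3.1.1 says that results for the blood biomarkers, including these two, "will be reported by the study intervention group at each visit in both Periods A and B". The repeated-measures model in SAP 2.8.3.2 also includes both markers, with visit as a categorical effect and an interaction between intervention and visit.

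**The concern.** The PD column has two windows for visits at which no PD draw is scheduled and none for the visit at which one is. The boundary between the two windows lies at the Week 10 target day. Two participants sampled one day apart, on Days 70 and 71, would be reported four weeks apart, and a draw exactly on target would be reported under a visit whose target is Day 85.

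At stake are the target-engagement results. Protocol 2.2.1.2.1 treats the rise in total TNF as reflecting target occupancy, and Protocol 4.3 uses total TNF concentrations in the dose rationale. As written, the by-visit tables, the time-profile plots and the repeated-measures model would give Week 8 and Week 12 results, each built mainly from part of the Week 10 draws, and no Week 10 result.

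**Working it through.** **1. Reproduce the target day.** Target day = 7 × week + 1. Week 10 gives 7 × 10 + 1 = Day 71, as in Table 15 and both protocol schedules. The permitted range is 71 ± 3, or Days 68 to 74.

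**2. Place each permitted day in the Table 15 windows.**

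| Day | PD Biomarker column | PK column |
|---|---|---|
| 68, 69, 70 | Week 8 (43–70) | Week 10 (64–77) |
| 71, 72, 73, 74 | Week 12 (71–98) | Week 10 (64–77) |

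None of the seven days can be labelled Week 10 for PD.

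**3. Could this be a broken table?** No. The PK windows run 50–63, 64–77, 78–98 without gaps, so 64–77 belongs to PK. As a PD window it would overlap both 43–70 and 71–98. The PD windows themselves adjoin (70 | 71) and leave no room for a third. Reading the two markers under the Blood biomarkers column gives the same result, because that column also has 43–70, 71–98 and no Week 10.

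**4. Why the boundary falls there.** The midpoint of the Week 8 and Week 12 targets is (57 + 85)/2 = 71. The PD column has the same Week 8 and Week 12 windows as the ADA and Blood biomarkers columns, while PK has its own Week 10 window. This suggests that the column was carried over. Table 9 of the SAP lists no such change.

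**5. Size of the split.** The documents give no distribution of actual visit days, so this rests on assumptions:

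| Assumption about Week 10 visit days | Labelled Week 8 | Labelled Week 12 |
|---|---|---|
| All on Day 71 or later | 0% | 100% |
| Rounded normal around Day 71, cut to ± 3 days, SD 0.5 | 16% | 84% |
| Same, SD 1 | 31% | 69% |
| Same, SD 3 | 41% | 59% |
| Even over Days 68–74 | 3/7 = 43% | 4/7 = 57% |

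With an even spread and complete data:
- 66 naïve participants: 66 × 3/7 ≈ 28 and 66 × 4/7 ≈ 38.
- About 22 of these on placebo (2:1 randomization): 22 × 3/7 ≈ 9 and 22 × 4/7 ≈ 13.
- About 84 in the safety population, used for the descriptive tables: 84 × 3/7 = 36 and 84 × 4/7 = 48.

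**6. Precision of a by-visit mean.** The standard error is proportional to 1/√n. Relative to one Week 10 visit, it is √(7/3) = 1.53 times as large at the Week 8 label and √(7/4) = 1.32 times at the Week 12 label.

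**7. Proposed window.** A single Week 10 window of Days 43–98 contains all of Days 68–74, starts the day after the Week 4 window ends (Day 42) and ends the day before the Week 16 window begins (Day 99). There is no gap or overlap.

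**The case against.** Several counter-arguments deserve a hearing.

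- **The Week 8 and Week 12 windows are not always empty.** Participants who stop treatment early have an EOT visit and then an EOS visit 8 weeks later, both with PD draws, and these can fall on Days 43–98. This stands as a qualification. It concerns off-schedule draws that any set of windows must place, and it does not give the Week 10 draw a correct label. Likewise, it is only PD draws that are unscheduled at Weeks 8 and 12; PK and other panels are sampled at one or both.
- **The 28/38 split is an assumption.** This is correct. It needs even spread and no missing samples. If every draw is on Day 71 or later, all share one label and no precision is lost, although that label is Week 12.
- **The standard-error ratios do not carry over to the model.** This is also correct. They describe simple by-visit means; the repeated-measures model has a participant-level random effect, so they are only approximate there.
- **The impact is small.** No sample is discarded, the model targets an overall effect using all data to Week 16, and the specifically named contrasts use Weeks 16, 28 and 36. PD markers are not primary or secondary endpoints, and OX40L was almost always below quantification in healthy volunteers. This limits the importance of the point but leaves the wrong visit results in place.
- **Days 43–98 is wide.** The midpoints to the neighbouring PD visits are (29 + 71)/2 = Day 50 and (71 + 113)/2 = Day 92, so Days 43–49 and 93–98 are nearer to Week 4 and Week 16. This is true, but those edges are the ones the SAP already uses for Weeks 4 and 16, and no on-schedule draw falls in these outer days.
- **The sentence introducing the windows does not name PD.** This has little weight, since Table 15 has a PD column.

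**Conclusion.** The concern holds. Under the SAP's own date rule, every on-schedule Week 10 draw of serum TNF and OX40L receives a wrong visit label: Week 8 if taken on Days 68–70, Week 12 if taken on Days 71–74. This conclusion needs no assumption beyond the ± 3-day visit window.

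The division between the two labels does depend on actual visit days. The share labelled Week 8 ranges from 0% (no draw before Day 71) to 43% (even spread) across the scenarios examined. Under even spread, the descriptive standard errors are 1.3 to 1.5 times those of one Week 10 visit. The consequence is confined to the by-visit PD summaries, their plots and the visit-specific terms of the PD model. It should be corrected before those analyses are run; it does not bear on the primary endpoint.

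**What to change.** In the PD Biomarker column of SAP Table 15, delete the Week 8 and Week 12 windows for Period A and enter Days 43–98 in the Week 10 row (target Day 71). Make clear that soluble TNF and OX40L follow this column and not the Blood biomarkers column, since SAP 2.8.3.1.1 lists them among the blood biomarkers. The Period A post-baseline visits with a scheduled PD draw (Weeks 4, 10 and 16) would then each have a window.

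A narrower window, such as the 64–77 already used for PK, would also capture every permitted Week 10 day. It would require removing the PD Week 8 and Week 12 windows, or cutting them back so that they do not overlap. With either choice, one added sentence saying how PD draws from an early EOT or EOS visit are assigned would settle the remaining ambiguity.

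The cost is an edit to one table column and, if adopted, those clarifying sentences. Sampling, sample size and the primary analysis do not change.

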2.8.3.1 Biomarkers-specific analyses

2.8.3.1.1 Blood biomarkers

Analysis of blood biomarkers will be performed for markers associated with HS and/or SAR442970 activity, including:

- sTNF (soluble Tumor Necrosis Factor)
- sOX40L (soluble OX40 Ligand)
- Lipocalin-2
- CRP (C-Reactive Protein)
- hsCRP (High-Sensitivity C-Reactive Protein)
- SAA (Serum Amyloid A)
- ASCA (Anti-Saccharomyces cerevisiae antibodies)
- ACPA (Anti-Citrullinated Protein Antibodies)
- Absolute neutrophil count
- ESR (Erythrocyte Sedimentation Rate)
- IL-6 (Interleukin-6)
- CXCL13 (C-X-C Motif Chemokine Ligand 13)
- YKL40

For all the blood biomarkers,

- descriptive statistics at baseline and under treatment (table),
- boxplots and/or time profile plots (means \pm SEM)

will be reported by the study intervention group at each visit in both Periods A and B. Both the raw analysis values, change and percent change from baseline will be reported. Data will be log-transformed as appropriate.

Additionally, for period B, fold change, percent change, and absolute change from Week 16 to Week 28 will be calculated for all biomarkers mentioned above. These analyses will compare participants from period A and B. Also, for sTNF and sOX40L, fold change, percent change, and absolute change from Week 16 to Week 36 will also be presented for both groups of participants.

2.8.3.1.2 Skin biopsy analyses

Optional punch biopsy of lesional and non-lesional skin will be performed for analysis by Immunohistochemistry (IHC). IHC is laboratory techniques used to detect specific proteins in tissue samples. This technique involves the use of antibodies that bind to target proteins, allowing

their visualization under a microscope. IHC is used to detect OX40 and OX40L proteins levels in participants under SAR442970 intervention.

Descriptive statistics for the change from baseline through Week 16 will be performed in histological features of lesional skin by Immunohistochemistry (IHC) for participants who consent to participate in this optional assessment. If we have fewer than 10 patients, a listing will be done instead.

Categorical data to be reported:

- H&E inflammation score (0-5)

Numerical data to be reported include but not limited to:

- H&E neutrophil infiltration %
- OX40 and OX40L – Adnexa (dermis) cellular density (cells/mm²)
- OX40 and OX40L – Epidermis % of positive inflammatory cells
- OX40 and OX40L – Adnexa in epidermis % of positive cells
- OX40 and OX40L – Dermis + Adnexa cellular density (cells/ mm²)

For categorical data:

- the number and frequency of each category will be tabulated by study intervention group and time point,
- a shift table of the number and percent of patients in each category at baseline vs. post-baseline

will be reported.

For numerical (percent and density) data:

- descriptive statistics at baseline and under treatment (table) of raw values, Change from baseline and Percent Change from baseline,
- boxplots

will be reported by study intervention group and visit.

